7.2.1 Other Information

Linaclotide is contraindicated in pediatric patients up to 6 years of age. This is because in nonclinical studies, administration of a single, clinically relevant adult oral dose of linaclotide caused deaths due to dehydration in young (Day 7 postpartum) juvenile mice. Supplemental subcutaneous fluid administration prevented death after linaclotide administration in neonatal mice, and significantly higher doses (\geq 10 times the clinically relevant adult dose) were tolerated in older juvenile mice without supplemental fluid administration.

In post-marketing experience, severe diarrhea AEs associated with dizziness, syncope, hypotension and electrolyte abnormalities (hypokalemia and hyponatremia) requiring hospitalization or intravenous fluid administration have been reported in patients treated with linaclotide.

This study will be the first to evaluate the safety and efficacy of linaclotide relative to placebo in pediatric patients, 7 to 17 years of age, with IBS-C.

8.0 STUDY OBJECTIVES

The objective of this study is to evaluate the dose response, safety, and efficacy of 4 weeks of treatment with 1 of 3 linaclotide doses (A, B, or C) or 290 ug (as an exploratory objective in the adolescent patients 12 - 17 years of age using the approved adult dose) compared with placebo in pediatric patients 7 to 17 years of age who fulfill the Rome III criteria for child/adolescent IBS and modified Rome III criteria for child/adolescent FC.

9.0 INVESTIGATIONAL PLAN

9.1 OVERALL STUDY DESIGN AND PLAN: DESCRIPTION

This clinical study will be a multicenter, randomized, double-blind, placebo-controlled, parallel-group, safety and efficacy study comparing 1 of 3 linaclotide doses (A, B, and C) or 290 ug (only patients 12 - 17 years of age) with placebo in pediatric patients, 7 to 17 years of age, with a diagnosis of IBS-C based on Rome III child/adolescent criteria (ie, fulfill Rome III criteria for child/adolescent IBS and fulfill modified Rome III criteria for child/adolescent FC). The study will include a total of 6 visits and will be approximately 9 to 12 weeks in duration (Figure 9.1.4-1). Approximately 260 patients with IBS-C will be enrolled in this study.

- Screening Period (14 to 28 days)
- Pretreatment Period (14 to 21 days)
- Double-blind Treatment Period (hereinafter referred to as Treatment Period) (at least 28 days [4 weeks] on treatment)
- Post-treatment Period (at least 7 days [1 week] after the Week 4 End-of-Treatment Visit)

[figure not shown]
9.1.1 Screening Period

After obtaining assent and informed consent (Section 5.3), patient eligibility for entry into the study will be determined (Sections 9.3.1 and 9.3.2). The Screening Period will begin up to 7 weeks before Randomization (Visit 3/Day 1) and will last for 14 to 28 days. Patients will not receive any investigational product during the Screening Period.

9.1.2 Pretreatment Period

The Pretreatment Period will occur up to 3 weeks before Randomization (Visit 3/Day 1) and will last for 14 to 21 days. Patients will not receive investigational product during the Pretreatment Period.

9.1.3 Double-blind Treatment Period

Patients will complete at least 4 weeks of investigational product treatment during the Double-blind Treatment Period (referred to as Treatment Period). Three study visits will occur during the Treatment Period: a Randomization Visit (Visit 3/Day 1), a Week 2 Visit (Visit 4, approximately Day 15) and a Week 4 End-of-Treatment-Period Visit (Visit 5, approximately Day 29). Randomization will occur on the first day of the Treatment Period. Based on randomization, patients will receive placebo or linaclotide. The first dose of investigational product will be administered at the study site following randomization (Visit 3/Day 1).

[figure not shown]

9.1.4 Post-treatment Period

The End-of-Study Visit (Visit 6/Post-treatment Visit) must occur at least 7 days after the Week 4 Visit (Visit 5). Patients will not receive investigational product during the Post-treatment Period, but will continue to complete the eDiary twice daily throughout the Post-treatment Period.

The figure below provides a schematic of the study design. The Schedule of Evaluations is presented in Section 2.0. Detailed descriptions of each study visit can be found in Section 9.5.1.

Figure 9.1.4-1. Study Design

Note: There is no Day 0.

a The patient must complete at least 4 weeks (28 days) of treatment before arriving at the study site for the Week 4 Visit.

b The Post-treatment Visit has to be at least 7 days after the Week 4 Visit.

9.2 DISCUSSION OF STUDY DESIGN, INCLUDING THE CHOICE OF CONTROL GROUPS

A multicenter, randomized, double-blind, placebo-controlled, parallel-group, safety and efficacy dose-ranging study design was chosen based on prior studies that established linaclotide efficacy and safety in adult patients with IBS-C. Additionally, this study was designed with reference to the FDA Guidance for Industry E11 Clinical Investigation of Medicinal Products in the Pediatric Population. In this pediatric study, Investigators will enroll patients 7 to 17 years of age with a diagnosis of IBS-C based on Rome III criteria for child/adolescent IBS and modified Rome III criteria for child/adolescent FC.

[figure not shown]
The linaclotide doses selected for use in this study were based on prior studies in adult patients with IBS-C, current product labeling for the treatment of IBS-C and/or CIC in North America (ie, US, Canada, and Mexico for both indications in adult patients) and the European Union (IBS-C only in adult patients), and communications with the FDA.

[figure not shown]
9.3 SELECTION OF STUDY POPULATION

9.3.1 Inclusion Criteria

To be eligible to participate in the study, patients must meet the following criteria:

1. Patient must provide written or verbal informed assent and the parent/guardian/LAR and caregiver must provide written informed consent before the initiation of any study-specific procedures (Section 5.3)
2. Patient is a male or female outpatient, weighing ≥ 18 kg, 7 to 17 years of age (inclusive) at the time the patient provides assent for the study and parent/guardian/LAR has provided signed consent

[figure not shown]

6. Patient meets Rome III criteria for child/adolescent IBS: at least once per week for at least 2 months before the Screening Visit, the patient experienced abdominal discomfort (an uncomfortable sensation not described as pain) or pain associated with 2 or more of the following at least 25% of the time:
 - a. Improvement with defecation
 - b. Onset associated with a change in frequency of stool
 - c. Onset associated with a change in form (appearance) of stool
7. Patient meets modified Rome III criteria for child/adolescent FC: For at least 2 months before the Screening Visit, the patient has had 2 or fewer defecations (with each defecation occurring in the absence of any laxative, suppository, or enema use during the preceding 24 hours) in the toilet per week

In addition, at least once per week, patient meets 1 or more of the following:

- a. History of retentive posturing or excessive volitional stool retention
- b. History of painful or hard bowel movements (BMs)
- c. Presence of a large fecal mass in the rectum
- d. History of large diameter stools that may obstruct the toilet
- e. *At least one episode of fecal incontinence per week*

8. Patient is willing to discontinue any laxatives used before the Pretreatment Visit in favor of the protocol-permitted rescue medicine ([Appendix III](#))

[figure not shown]
11. Patient has an average of fewer than 3 spontaneous BMs (SBMs) per week during the 14 days before the randomization day and up to the randomization (including the morning eDiary assessments reported before administration of first dose of double-blind investigational product on the randomization day). An SBM is defined as a BM that occurs in the absence of laxative, enema, or suppository use on the calendar day of the BM or the calendar day before the BM
12. Patient or parent/guardian/LAR or caregiver is compliant with eDiary by completing both the morning and evening assessments for **10** out of the 14 days immediately preceding the Randomization Visit (Section 9.1.2)

9.3.2 Exclusion Criteria

Patients who meet any of the following criteria will not be eligible to participate in the study:

[figure not shown]
1. Patient reports having more than 1 loose, mushy stool (eDiary-recorded stool consistency of 6 on the Pediatric Bristol Stool Form Scale [p-BSFS]) or any watery stool (eDiary-recorded stool consistency of 7 on the p-BSFS) with any SBM that occurred in the absence of laxative use on the calendar day of the BM or the calendar day before the BM during the 14 days before the randomization day and up to the randomization

[figure not shown]

6. Patient has required manual disimpaction anytime prior to randomization or disimpaction during in-patient hospitalization within 1 year prior to randomization

16. Patient is unable to tolerate the placebo prior to randomization

9.3.3 Removal of Patients from Therapy or Assessment

A premature discontinuation will occur when a patient who gave voluntary assent and whose parent/guardian/LAR and caregiver gave consent ceases participation in the study, regardless of circumstances, before the completion of the study visits and procedures. Patients will be prematurely discontinued from the study for reasons of safety including those who experience an SAE considered by the Investigator or the Sponsor to be related to investigational product. Patients will also be prematurely discontinued from the study for evidence of significant volume depletion and/or significant electrolyte and/or ECG abnormalities that are considered by the Investigator or Sponsor to be related to diarrhea related to the investigational product [REDACTED]

[REDACTED]. The Investigator should contact the Study Physician if there is any question whether the criteria for an AE [REDACTED] have been met and the patient should be discontinued from the study.

Patients can also be prematurely discontinued from the study after careful consideration for one of the following reasons:

- Screen failure (failure to meet inclusion/exclusion criteria)
- Withdrawal of consent
- AE
- Lack of efficacy
- Protocol violation
- Noncompliance with investigational product
- Lost to follow-up

- Study terminated by Sponsor
- Site terminated by Sponsor
- Other

All randomized patients who prematurely discontinue from the study, regardless of cause, should be seen for the assessments to be completed at the End-of-Treatment Visit (Week 4/Visit 5). The end-of-treatment assessments are defined as completion of the evaluations scheduled for all patients at Week 4 (Visit 5). In addition to the end-of-treatment assessments, all patients discontinuing the study prematurely should enter the Post-treatment Period and complete a Post-treatment Visit (Visit 6).

Patients who discontinue from the study and do not return to the study site for Visit 5 and/or Visit 6 must be requested in writing to return to the study site for procedures in Visit 5 or Visit 6 and return any unused investigational product and the handheld eDiary. A copy of the letter, together with the source documentation, will be kept in the Investigator's files. The reason for premature discontinuation from the study will be recorded on the Study Termination Page of the eCRF. Study site staff will be contacted by the Sponsor after each premature discontinuation to ensure proper characterization of the reason for discontinuation is captured.

9.3.4 Patient Replacement Procedures

Patients in this study who prematurely discontinue treatment will not be replaced.

9.4 TREATMENTS

Patients meeting the eligibility criteria during Visit 3 (Day 1) will be randomized in a double-blind fashion to linaclotide or placebo ([Table 9.4.5-1](#)).

Randomization will be stratified by age group:

- Patients 7 to 11 years of age will be randomized to linaclotide doses (A, B, or C) or placebo in a 1:1:1:1 allocation
- Patients 12 to 17 years of age will be randomized to linaclotide doses (A, B, or C, or the approved adult dose, 290 ug) or placebo in a 1:1:1:1:1 allocation

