Diagnosis and Main Criteria for Inclusion	Male and female pediatric patients 7 to 17 years of age with a diagnosis of irritable bowel syndrome with constipation (IBS-C) based on the Rome III criteria for child/adolescent IBS and modified Rome III criteria for child/adolescent FC
Test Product, Dosage, and Mode of Administration	Patients 7 to 11 years of age: linaclotide liquid oral solution or solid oral capsule taken once daily Patients 12 to 17 years of age: linaclotide solid oral capsule taken once daily Dosage is weight-based within the 7 to 11 years of age group: Patients 7 to 11 years of age (weight 18 to < 35 kg) 
Dose A: 18 ugDose B: 36 ugDose C: 72 ug Patients 7 to 11 years of age (weight \geq 35 kg) 
Dose A: 36 ugDose B: 72 ugDose C: 145 ug Patients 12 to 17 years of age 
Dose A: 36 ugDose B: 72 ugDose C: 145 ugApproved adult dose: 290 ug (for safety) [REDACTED]
Duration of Treatment	The study will be approximately 9 to 12 weeks in duration: up to a 4-week (14 - 28 days) Screening Period, a 2- to 3-week (14 to 21 days) Pretreatment Period, followed by a 4-week (\geq 28 days) Double-blind Treatment Period, and finally followed by a 1-week (\geq 7 days) Post-treatment Period. Patients will not receive investigational product during the Pretreatment Period or the Post-treatment Period.

Reference Therapy, Dosage, and Mode of Administration	Patients 7 to 11 years of age: matching placebo liquid oral solution or solid oral capsule taken once daily Patients 12 to 17 years of age: matching placebo solid oral capsule taken once daily
Criteria for Evaluation	
Primary Outcome Measure	Bowel movement (BM) characteristic assessments that determine the occurrences of spontaneous bowel movements (SBMs) (ie, BM frequency and rescue medication use) recorded morning and evening in either the patient- or interviewer-administered version of the handheld electronic diary (eDiary)
Key Secondary Outcome Measure	Evening assessment of abdominal pain daytime symptoms as recorded in the eDiary
Safety Measures	Adverse event recording, clinical laboratory tests, vital sign measurements including weight, electrocardiograms, and physical examinations
Pharmacokinetic Analysis	Individual plasma concentrations of linaclotide and its active metabolite (MM-419447) will be listed by patient.

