Statistical Methods	
The primary efficacy parameter is change from baseline in 4-week overall SBM frequency rate (SBMs/week) during the Treatment Period.
 
No multiplicity adjustment will be applied in this dose-ranging study. To understand the dose-response relationship, a test for linear trend will be performed for the primary efficacy parameter based on the ordinal dosing.
 
The key secondary efficacy parameter is change from baseline in 4-week abdominal pain daytime symptoms based on evening assessments during the Treatment Period. This key secondary efficacy parameter and other change-from-baseline secondary efficacy parameters defined for the Treatment Period will be analyzed in the similar way as the primary efficacy parameter (with A, B, and C linaclotide doses and placebo).
 
All safety parameters will be analyzed descriptively based on the Safety Population, defined as all randomized patients who receive at least 1 dose of double-blind investigational product. All efficacy analyses will be based on the Intent-to-Treat Population, defined as all patients in the Safety Population who have at least 1 postbaseline entry of BM assessments that determine occurrences of SBMs (ie, BM frequency and rescue medication use).
 
The planned sample size is designed for the overall analysis of placebo and A, B, and C linaclotide dose groups, with 58 patients per treatment group (232 patients in total for the overall analysis). With the inclusion of an additional 23 to 31 patients 12 to 17 years of age for the approved adult linaclotide dose, 290 ug, the planned sample size for the study is approximately 260 patients.

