9.4.4 Selection of Dosages in the Study

The doses chosen for this dose-ranging pediatric study are based on results obtained in the adult linaclotide clinical development program. In the adult program, 290 ug once daily was approved for IBS-C. Pediatric patients 7 to 11 years of age will be dosed using a weight-based approach; patients will receive 1 of 3 linaclotide doses. For patients weighing < 35 kg, the doses administered will correspond to about 0.5 to 1, 1 to 2, or 2 to 4 ug/kg. For patients weighing \geq 35 kg, the doses will not exceed 1, 2, or 4 ug/kg. Pediatric patients 12 to 17 years of age will receive 1 of 4 linaclotide doses. The approved adult dose, 290 ug for IBS-C, will be evaluated to obtain safety data in older pediatric patients ([Table 9.4.5-1](#)).

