9.4.5 Selection and Timing of Dose for Each Patient

All investigational products will be administered orally as a single daily dose, [REDACTED]

[REDACTED]

Dosage will be determined by weight for patients 7 to 11 years of age (18 to < 35 kg or ≥ 35 kg) (Table 9.4.5-1).

[REDACTED]

Table 9.4.5-1. Double-blind Dosing Regimen

Age Group	Weight	4-Week Treatment Period			
		Linaclotide Dose A	Linaclotide Dose B	Linaclotide Dose C	Approved Adult Dose
Patients 7 - 11 years^a					
18 - < 35 kg	18 ug	36 ug	72 ug	—	
	placebo	placebo	placebo	—	
	36 ug	72 ug	145 ug	—	
	placebo	placebo	placebo	—	
Patients 12 - 17 years^b					
	36 ug	72 ug	145 ug	290 ug ^c	
	placebo	placebo	placebo	placebo	

a Patients 7 to 11 years of age will receive linaclotide or placebo in a liquid oral solution or solid oral capsules.

b Patients 12 to 17 years of age will receive linaclotide or placebo in a solid oral capsule.

c Approved adult dose is for safety and exploratory efficacy only.

The Investigator may allow a patient to stop taking investigational product for up to 3 days because of an intolerable AE. If the Investigator believes that the patient is unable to resume dosing after 3 days, or requires a suspension of dosing on more than 1 occasion, the Investigator is required to contact the Study Physician to discuss the patient's continued participation in the study.

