9.7.5.1 Primary Efficacy Parameter

The primary efficacy parameter is the change from baseline in 4-week overall SBM frequency rate (SBMs/week) during the Treatment Period. The numerator of the SBM rate (SBMs/week) during the Treatment Period will be derived based on the total number of SBMs a patient reported during this period in the morning and evening eDiaries.

For the primary efficacy parameter, comparison between each linaclotide dose (A, B, and C) and placebo will be performed using an analysis of covariance (ANCOVA) model with treatment and age group (7 - 11 years of age and 12 - 17 years of age) as factors and baseline value as a covariate.

9.7.5.2 *Secondary Efficacy Parameters*

Key Secondary Efficacy Parameter

The key secondary efficacy parameter is change from baseline in 4-week abdominal pain daytime symptoms based on evening assessment of abdominal pain symptoms.

Abdominal pain scores will be collected twice daily in the eDiary: in the morning when a patient wakes up and in the evening at bedtime. Patients are asked to rate their abdominal pain from the time the patient wakes up until bedtime as part of the evening assessment, and a 5-point rating scale is derived from the patient's responses. The patient's 4-week abdominal pain daytime symptoms during the Treatment Period are defined as the average of the nonmissing daily abdominal pain daytime symptoms reported in evening assessments in the eDiary during the 4-week Treatment Period.

Other Secondary Efficacy Parameters

Four change from baseline parameters are additional secondary efficacy parameters in this study. Their description and analyses are provided below.

Change From Baseline in 4-Week Stool Consistency

Stool consistency will be collected twice daily in the eDiary, in the morning when a patient wakes up and in the evening at bedtime, and measured using the 7-point p-BSFS. The patient's p-BSFS score in the 4-week Treatment Period will be the observed weighted average of the daily p-BSFS scores (using weight of 1 for full day and 0.5 for half day) and the denominator in the observed weighted average will be the sum of the weights during this period. The daily p-BSFS score will be the average of nonmissing morning and/or evening assessments of the p-BSFS score from the SBMs reported by the patient on that specific day during the Treatment Period.

Change From Baseline in 4-Week of Severity of Straining

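### Weight band sets the dose at ages 7-11 but is in neither the stated strata nor the ANCOVA: a modest, cheaply avoided loss of precision and of protection against chance imbalance

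*Protocol*

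**What the plan says.** **Dosing.** Protocol Section 9.4.5 states: "Dosage will be determined by weight for patients 7 to 11 years of age". The Synopsis gives the amounts for A/B/C: 18/36/72 ug at ages 7-11 and 18 to <35 kg; 36/72/145 ug at ages 7-11 and ≥35 kg; 36/72/145 ug at ages 12-17, with no weight split. That makes three dosing bands.

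**Reason for the bands.** Section 9.4.4 ties the letters to body weight: "For patients weighing < 35 kg, the doses administered will correspond to about 0.5 to 1, 1 to 2, or 2 to 4 ug/kg". At 35 kg or more the doses are described as capped at 1, 2 or 4 ug/kg.

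**Randomisation.** Section 9.4: "Randomization will be stratified by age group". One bullet per age group follows, and neither names a weight stratum. For the younger group it reads: "Patients 7 to 11 years of age will be randomized to linaclotide doses (A, B, or C) or placebo in a 1:1:1:1 allocation".

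**Analysis.** Section 9.7.5.1 specifies an ANCOVA "model with treatment and age group (7 - 11 years of age and 12 - 17 years of age) as factors", with the baseline value as covariate. Section 9.7.5.2 uses the same terms for the other change-from-baseline parameters. In the Synopsis, under Statistical Methods, "a test for linear trend will be performed for the primary efficacy parameter based on the ordinal dosing".

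**Not visible.** Most of Section 9.4.3 (assignment method) and parts of Sections 9.4.5 and 9.7.5 are blacked out.

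**The concern.** The dosing scheme has three bands, while the visible strata and model terms distinguish two groups. The omitted split, under or over 35 kg at ages 7-11, separates smaller from larger children and halves the microgram dose (18 against 36, 36 against 72, 72 against 145 ug). If it is related to the change in SBM rate, two things follow. The variation it explains stays in the residual error. And in this one trial a dose arm may by chance hold noticeably more or fewer light children than placebo, with nothing in the model to correct for it.

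The pooled comparison of placebo with A, B and C is the one that Section 9.7.5 names for the main objective, so any such loss falls on the central result. The band must be known before the first dose, because it fixes the dose, and it is defined for placebo patients too. It is therefore a legitimate baseline covariate that is already to hand.

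**Working it through.** **1. Sample size in the plan.** 4 × 58 = 232 for the overall analysis. Adding 23 to 31 on 290 ug gives 255 to 263, which agrees with approximately 260 (Section 9.7.9).

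**2. Children aged 7-11 per arm.** Adolescents are allocated 1:1:1:1:1 (Section 9.4), so 23-31 on 290 ug implies 23-31 adolescents in each other arm. That leaves 58 − 31 = 27 to 58 − 23 = 35 children aged 7-11 per arm, a share of 27/58 = 0.47 to 35/58 = 0.60.

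**3. Chance imbalance.** Let p be the share of 7-11-year-olds under 35 kg. The protocol does not give it; I assume 0.3 to 0.7. With stratification by age group only, the number of light children in an arm is treated as binomial(n, p).

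- 95% range of the difference between two arms: ±1.96 × √(2p(1−p)/n). For n = 27, p = 0.5 this is ±1.96 × √(0.5/27) = ±0.267. For n = 35, p = 0.3 or 0.7 it is ±1.96 × √(0.42/35) = ±0.215. The range is thus about ±21 to 27 percentage points among 7-11-year-olds.
- Exact binomial probability of a difference of 20 points or more, over every n from 27 to 35 and p from 0.3 to 0.7: 7-16% for one dose-placebo pair, and 17-35% for at least one of the three pairs, which share the placebo arm.

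**4. What a 20-point imbalance does.** Shift in the whole-arm contrast = share aged 7-11 × 0.20 × band effect. With an assumed band effect of 0.3-0.8 SD, this runs from 0.47 × 0.20 × 0.3 = 0.03 SD to 0.60 × 0.20 × 0.8 = 0.10 SD. The standard error of one contrast is about √(2/58) = 0.19 SD.

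**5. Residual variance.** Variance added by leaving the band out = share × p(1−p) × (band effect)², in units of the within-band variance.

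| Case | Share | p(1−p) | Effect² | Added variance | × 232 |
|---|---|---|---|---|---|
| Low | 0.47 | 0.21 | 0.09 | 0.009 | about 2 |
| High | 0.60 | 0.25 | 0.64 | 0.097 | about 22 |

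So about 1-10%, worth about 2-22 patients.

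**6. Simulation of the ANCOVA with and without the band.** 3,000 runs per setting, 58 per arm, 31 of them aged 7-11, p = 0.5, true treatment effect 0 or 0.5 SD.

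| Band effect | SD of contrast, without → with band | Power at 0.5 SD, without → with band |
|---|---|---|
| 0.5 SD | 0.190 → 0.188 | 74.2% → 74.7% |
| 1.0 SD | 0.195-0.200 → 0.188 | 71.8% → 76.7% |

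The mean estimates stayed on target and the type I error was 5.1-5.3% in both models. The 1.0 SD row lies above the range assumed in step 5.

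**The case against.** The best defence is that this is an acceptable choice in a phase 2 dose-ranging study that reports nominal p-values, and much of it stands.

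- **The letters are weight-scaled by design.** A reader might infer that the plan mislabels doses because 36 ug is Dose B for a lighter child and Dose A for a heavier one, and 72 ug is C or B. Section 9.4.4 does not support that: the bands keep the dose per kilogram roughly comparable within a letter, and the trend test is stated on ordinal dose. Calling the mixture a flaw presumes that micrograms are the right scale.
- **Validity is not at stake.** A reader might infer that the contrasts are biased. They are not: randomisation balances the band in expectation, and the type I error is unaffected. Ordinary standard errors already allow for chance imbalance of this size, and a shift of 0.03-0.10 SD is small against 0.19 SD.
- **The gain may be very small.** At a band effect of 0.5 SD, power moves by half a point. The protocol gives neither the band effect nor the share under 35 kg.
- **Redaction.** A further stratum or a weight analysis may sit in the blacked-out text. That limits the point to the visible strata and model terms, which name no weight band.
- **The SAP.** By-band descriptive tables are usual SAP content, so their absence is no finding. The model terms are different: the protocol itself fixes them.

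None of this argues against a covariate that is known before dosing, contains the randomisation stratum and costs one degree of freedom.

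**Conclusion.** The point holds as a modest improvement worth making, not as an error that threatens the trial. The visible text omits from both strata and model the variable that sets the dose at ages 7-11. The loss is of precision and of protection against chance imbalance in a single trial. Its size rests on two assumptions: 30-70% of 7-11-year-olds under 35 kg for the imbalance figures, and additionally a band effect of 0.3-0.8 SD for the variance figure. If the band is unrelated to outcome, nothing is lost by the present model and essentially nothing by the proposed one: with a band effect of 0, simulated power was 77.1% without the term and 76.8% with it.

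**What to change.** In Sections 9.7.5.1 and 9.7.5.2, replace the two-level age-group factor by a three-level dosing-band factor: 7-11 years and 18 to <35 kg; 7-11 years and ≥35 kg; 12-17 years. Use the same factor in the linear-trend test. The new factor nests the age stratum, so the analysis still respects the stratified randomisation.

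The cost is one model degree of freedom and a wording change, with no added patients, visits or procedures. The change should be made before unblinding. It adjusts for prognosis only: each letter at ages 7-11 will still combine two microgram amounts, as the design intends. No mid-study change to the randomisation is needed; at Amendment 3 it would leave patients randomised under two schemes.
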